9.8.6 Retention Samples

Serum and plasma samples will be collected for future analysis by sites with access to a -70/80°C freezer only. No genetic testing will be completed on any samples obtained during the study. Samples will be stored for a maximum of 5 years following the last study sample taken. Analyses will be restricted to safety related analyses and exploratory efficacy related analyses of ferric maltol related to the treatment of IDA.

9.8.7 Urine Pregnancy Test

Females of childbearing potential only. A urine pregnancy test should be conducted using kits provided by the central laboratory.

10 SAFETY

10.1 DEFINITIONS

10.1.1 ADVERSE EVENT (AE)

An AE is any untoward medical occurrence in a subject administered a pharmaceutical product and does not necessarily have a causal relationship with this treatment. An AE can therefore be any unfavourable or unintended sign or symptom, intercurrent illness, injury, or any concomitant impairment of the subject's health, temporally associated with the use of a medicinal product, whether or not considered related to the medicinal product.

A treatment-emergent AE is any AE temporally associated with the use of a study drug, whether or not considered related to the study drug.

AEs include:

- Exacerbation of a chronic or intermittent pre-existing condition/disease/symptoms present at baseline that worsen during the study including either an increase in frequency and/or intensity.
- Disease or medical condition detected or diagnosed after study drug administration even though it may have been present prior to the start of the study.
- Events considered by the Investigator to be related to study-mandated procedures.
- Abnormal safety assessments, e.g. laboratory test abnormalities, physical exam findings, ECG or vital sign measurements must be reported as AEs if they represent a clinically significant finding in the medical and scientific judgment of the Investigator, symptomatic or not, which was not present at baseline or if present at baseline, worsened during the course of the study or led to dose reduction, interruption or permanent discontinuation of study drug. However, if an abnormal laboratory or other safety-related test result is associated with clinical signs or symptoms, the signs or symptoms should be recorded as an AE. If signs and symptoms are part of a diagnosis, then the diagnosis should be recorded as AE.
- Signs, symptoms of a suspected drug interaction.
- Signs, symptoms of a suspected overdose of either the study drug or a concomitant medication (overdose per se will not be reported as AE/SAE).

AEs do not include:

- Medical or surgical procedure, e.g., surgery, appendectomy, endoscopy, tooth extraction, transfusion (as these are treatments for an AE). However, the event resulting in the procedure is an AE (e.g. appendicitis, abdominal pain).
- Pre-existing disease or medical condition documented at baseline that does not worsen.
- Situations in which an adverse change did not occur, e.g., hospitalisations for cosmetic elective surgery or for social and/or convenience reasons.
- Anticipated day-to-day fluctuations or seasonal fluctuations (e.g. allergic rhinitis) of pre-existing disease(s) or condition(s) documented at baseline.
- The disease/disorder being studied, or the expected progression, signs or symptoms (including laboratory values) of the disease/disorder being studied, unless it is more severe than expected for the subject's condition.

- Overdose of either study drug or concomitant medication without any signs or symptoms.

10.1.2 SERIOUS ADVERSE EVENT (SAE)

An SAE is any untoward medical occurrence between the time of consent and the subjects final visit that:

- is fatal,
- is life-threatening,
- requires inpatient hospitalisation or prolongation of existing hospitalisation,
- results in persistent or significant disability/incapacity,
- results in a congenital anomaly/birth defect or
- is otherwise judged as medically significant (may jeopardise the subject).

The following guidelines should be used:

Life-threatening: Refers to an event in which the subject was at risk of death at the time of the event; it does not refer to an event which hypothetically might have caused death if it were more severe.

Inpatient hospitalisation: Subject has to stay in hospital at least overnight. The following reasons for hospitalisations are not considered AEs, and therefore not SAEs:

- Hospitalisations for cosmetic elective surgery, social and/or convenience reasons. Standard monitoring of a pre-existing disease or medical condition that did not worsen, e.g., hospitalisation for coronary angiography in a subject with stable angina pectoris.
- Elective treatment of a pre-existing disease or medical condition that did not worsen, e.g., hospitalisation for chemotherapy for cancer, elective hip replacement for arthritis, vein stripping for preventive and/or cosmetic purpose.

Prolongation of hospitalisation: Complications that occur during hospitalisation are AEs. However, if a complication prolongs hospitalisation or would have required hospitalisation or fulfils any other serious criteria, that complication is considered an SAE. In any case, admission to an intensive care unit is considered a prolongation of hospitalisation. When in doubt as to whether “prolongation of hospitalisation” was necessary, the AE should be considered serious.

Significant disability: The term significant disability means that there is a substantial disruption of a person’s ability to conduct normal life functions. This definition is not intended to include experiences of relatively minor medical significance such as uncomplicated headache, nausea, vomiting, accidental trauma (e.g. sprained ankle) or uncomplicated chronic diseases which may interfere or prevent everyday life functions but do not constitute a substantial disruption.

Medically significant: Medical and scientific judgment should be exercised in deciding whether other situations should be considered serious, such as, important medical events that might not be immediately life-threatening or result in death or hospitalisation but might/may jeopardize the subject or might/may require intervention to prevent one of the other outcomes listed in the definition above. Examples of such events are invasive or malignant cancers, intensive treatment in an emergency room or at home for allergic bronchospasm, blood dyscrasias or convulsions that do not result in hospitalisation, or development of drug dependency or drug abuse.

SAE related to study-mandated procedures: Such SAEs are defined as SAEs that appear to have a reasonable possibility of causal relationship (i.e., a relationship cannot be ruled out) to study-mandated procedures (excluding administration of study drug) such as discontinuation of subject's previous treatment during a washout period, or complication of a mandated invasive procedure (e.g., blood sampling, heart catheterization), or car accident on the way to the hospital for a study visit, etc.

10.2 REPORTING AND DOCUMENTATION

AEs should be documented in terms of a medical diagnosis. When this is not possible, the AE should be documented in terms of signs and/or symptoms observed by the Investigator or reported by the subject at each study visit.

Any pre-existing conditions or signs and/or symptoms present in a subject prior to the start of the study should be recorded on the Medical History CRF.

All SAEs that occur after informed consent is obtained through study completion or premature discontinuation must be documented on the AE form in the CRF and reported to the Sponsor via an SAE form within 24 hours of awareness. All AEs occurring from the time of the first dose of study treatment through study completion or premature discontinuation must be documented on the AE form in the CRF.

Any SAE that occurs during the clinical study or within two weeks of receiving the last dose of study drug, whether or not related to the study drug, must be reported to the Sponsor.

Deaths or congenital abnormalities if brought to the attention of the Investigator AT ANY TIME after cessation of study drug AND considered by the Investigator to be possibly related to study drug, should be reported to the Sponsor.

At each visit AEs will be solicited. The nature of each event should be established. Details of changes to study drug dosing or any subsequent treatment should be recorded on the appropriate pages of the CRF.

AEs already documented in the CRF (i.e., at a previous assessment) and designated as 'ongoing' should be reviewed at subsequent visits as necessary. Upon resolution, the date of resolution should be recorded in the CRF. If an AE increases in frequency or severity during a study period, a new record of the event should be started. If the AE lessens in intensity, no change in the intensity is required as only the worst intensity must be reported

All AEs and SAEs, including those that are ongoing at the end of the study or at premature discontinuation, will be followed up until resolution or stabilization or until the event is otherwise explained.

10.2.1 Immediate Reporting

The following AEs must be reported within 24 hours to the Sponsor or designee:

- SAEs
- Pregnancy (not considered as an AE, but must be reported immediately)

For immediate reporting, the Investigator must fill out the SAE form (also for pregnancies) and send to the Sponsor within 24 hours after awareness.

SAFETY CONTACT DETAILS

Primevigilance Limited has been contracted by the Sponsor for safety reporting

Email SAE reports to [contact] or fax to [name]

Contact details for safety questions will be provided in the Investigator Site File

If the site obtains relevant follow-up information, this information needs to be forwarded to the Sponsor within 24 hours of awareness using a new SAE form and the updated AE form if appropriate.

Other documents must be submitted upon request. All documents must be blinded with respect to the subject's personal identification to meet data protection requirements, e.g., on the discharge summary this data must be blinded and the subject number added.

As soon as the Sponsor is informed about an SAE, an evaluation and potential reporting to central IRBs/ECs, competent authorities and other concerned parties will occur as required. The Investigator will be responsible for reporting to any local IRB/EC as required.

10.2.2 Non-Immediate Reporting

AEs that do not qualify for immediate reporting will be documented in the CRF and reported in the Clinical Study Report (CSR).

10.3 EVALUATION

AEs and the corresponding entries in the CRF will be reviewed by the Investigator or qualified member of the study staff.

10.3.1 Intensity

The intensity will be rated by the Investigator as "mild", "moderate" or "severe":

Mild: Symptoms barely noticeable to the subject or does not make the subject uncomfortable; does not influence performance or functioning.

Moderate: Symptoms of a sufficient severity to make the subject uncomfortable; performance of daily activity is influenced; subject is able to continue in study.

Severe: Symptoms cause significant discomfort; incapacitation or significant impact on the subject's daily life; may cause cessation of study treatment.

A mild, moderate or severe AE may or may not be serious. These terms are used to describe the intensity of a specific event (as in mild, moderate, or severe myocardial infarction). However, a severe event may be of relatively minor medical significance (such as severe headache) and is not necessarily serious. For example, nausea lasting several hours may be rated as severe, but may not meet the definition of seriousness. Fever of 39 °C that is not considered severe may become serious if it prolongs hospitalisation.

10.3.2 Causality

The following should be considered when evaluating the relationship of AEs and SAEs to the study treatment:

Not related: There is not a possibility that the event has been caused by the product under investigation. Consideration should be given to factors, including but not limited to, a lack of reasonable temporal relationship between administration of the drug and the event, the presence of a biologically implausible relationship between the product and the AE (e.g. the event occurred before administration of drug), or the presence of a more likely alternative explanation for the AE.

Related: There is a possibility that the event may have been caused by the product under investigation. Consideration should be given to factors, including but not limited to a positive re-challenge, a reasonable temporal sequence between administration of the drug and the event, a known response pattern of the suspected drug, improvement following discontinuation or dose reduction, a biologically plausible relationship between the drug and the AE or a lack of an alternative explanation for the AE.

10.3.3 Outcome

The outcome of each AE has to be assessed as follows:

- Fatal: The AE resulted in death ("Death" is recorded as an outcome, not as the AE)
- Ongoing/Not resolved: The AE has not resolved
- Recovered with sequelae: Resolution of the AE has occurred, but the subject retains some sequelae
- Recovered: The AE fully resolved with no observable residual effects
- Unknown: The outcome of the AE is not known as the subject did not return for follow-up and attempts to locate the subject and/or to obtain follow-up information were unsuccessful (lost to follow-up).

10.4 RE-EXPOSURE

If an AE requires discontinuation of IMP and is judged to be treatment-related by the Investigator or by the Sponsor, re-exposure is not allowed. If an AE requires dose reduction or discontinuation of IMP and is judged by the Investigator or by the Sponsor to be unrelated to investigational products, the decision to re-introduce the medication or to increase the dose of the medication requires prior approval of the Sponsor or designee.

10.5 SAFETY ENDPOINTS

During the study, safety endpoints will include treatment-emergent AEs and SAEs including clinically significant changes from baseline in vital signs, body weight, laboratory or ECG abnormalities.

11 STATISTICAL CONSIDERATIONS

11.1 SAMPLE SIZE AND POWER CALCULATIONS

A sample size of 135 subjects (Randomized 2:1, ferric maltol:Placebo, 90 in ferric maltol group and 45 placebo) will have 95% power to detect a statistically significant treatment difference of 1.0g/dL between ferric maltol and placebo on the primary endpoint, using a two-sided 0.05 significance level. This calculation assumes a common standard deviation of 1.5g/dl which is based on a pooled estimate of SDs obtained from published trials (Feraheme prescribing information 2010; Quinibi 2011; Macdougall 2014 Schwenk 2010; Singh 2006; Wyck 2005). Assuming a drop-out rate of 20%, approximately 168 subjects total will be recruited. Subjects randomization will be stratified based on baseline Hb value and eGFR.

11.2 STATISTICAL METHODS

11.2.1 Primary Endpoint Analysis

Effectiveness will be analysed by determining whether the Test group shows a statistically significant superiority as compared to the Control group.

An Analysis of Covariance (ANCOVA) will be used to analyse the primary endpoint: change in Hb concentration from baseline to Week 16. Missing change from baseline hemoglobin concentration data for week 16 will be imputed using multiple imputation methodology. This will generate 10 complete datasets containing imputed values for those missing in the original dataset. Hb concentrations at baseline, Week 4, Week 8 and gender will be considered as variables helpful in guiding this imputation. For each imputed dataset, the change from baseline to Week 16 complete datasets will be analysed using ANCOVA with factors for treatment and disease and a covariate of baseline hemoglobin and eGFR. By combining the results from these analyses, the treatment estimates will be constructed using the parameter estimates and associated standard errors. Similarly the difference of the adjusted treatment means (ferric maltol – placebo) will be presented with the associated standard error and 2-sided 95 % confidence interval.

The primary endpoint analysis will be performed using the intention-to-treat (ITT) population.

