- Open-label Treatment: Up to 36 weeks treatment with ferric maltol.
- End of Study: Week 52 or premature discontinuation.
- Post-treatment safety follow-up: 14 days following discontinuation of study medication.

Subjects that develop a ≥ 0.5 g/dL decrease from baseline in Hb that falls below 8.0g/dL on 2 consecutive weeks will be discontinued from study treatment.

Subjects who discontinue from study treatment prior to Week 16 will be encouraged to continue with study visits and assessments up to and including assessments at week 16.

Number of Subjects

Approximately 168 subjects.

Inclusion Criteria

All of the following criteria must be met to randomize a subject in the study:

1. Ability to understand the information given in the Independent Ethics Committee (IEC) or Institutional Review Board (IRB) approved information sheet and consent form. Must sign and date the informed consent and authorization to use protected health information (PHI) in accordance with national and local subject privacy regulations prior to any study mandated procedure.
2. Willing and able to comply with study requirements.
3. Age ≥ 18 years at the time of informed consent.
4. A current diagnosis of CKD with an estimated glomerular filtration rate (eGFR) of <60 mL/min/1.73m² and ≥ 15 mL/min/1.73m², as calculated using the abbreviated version of the Modified Diet in Renal Disease equation (MDRD) assessed via screening laboratory results.
5. Iron deficiency anemia defined by the following criteria assessed via screening laboratory results:
 - a. Hb <11.0 g/dL and ≥ 8.0 g/dL
 - b. AND ferritin <250 ng/mL with a Transferrin saturation (TSAT) $<25\%$
OR ferritin <500 ng/mL with a TSAT of $<15\%$
6. Female subjects of childbearing potential (including perimenopausal females who have had a menstrual period within 1 year prior to screening) must agree to use a reliable method of contraception until study completion

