4.4 DOSE SELECTION AND RESULTS OF PREVIOUS CLINICAL STUDIES

Ferric maltol is not absorbed systemically as an intact complex and traditional PK studies may not provide the relevant information (Barrand 1991). Therefore, a model was developed to determine the optimal dose. Data from 6 previous studies of ferric maltol in subject with IBD and IDA were used to estimate absorption rates in the study population. Using these data, the model suggested that in a compliant study population, 30 mg ferric maltol bid would result in correction of baseline anemia in the majority of subjects.

An open-label, randomized Phase 1 study evaluated the pharmacokinetics of ferric maltol and its effect on iron indices in IBD patients with iron deficiency (with or without anemia). Twenty four subjects received ferric maltol 30, 60, or 90 mg bid over an 8-day period. Pharmacokinetics and iron uptake were assessed on Days 1 and 8. Ferric maltol showed predictable pharmacokinetics, with linear increases in exposure, no accumulation over 7 days, and improvements in iron uptake across the dose range 30–90 mg bid.

The dose chosen for Phase 3 studies is 30 mg bid ferric maltol, or 60 mg elemental iron total daily dose.

A Phase 3 study has been completed in subjects with IDA and Inflammatory Bowel Disease (IBD), who are intolerant of oral iron products or are unsuitable for treatment with them (ST10-01-301 and ST10-01-302; Gasche 2014). 128 subjects were randomized to 12 weeks of blinded medication (30mg bid ferric maltol or matched placebo capsule) followed by a 52 week open-label extension period; during which all available subjects received ferric maltol at the same dose. 87% and 82% ferric maltol and placebo treated subjects, respectively, completed the 12 week double blind period. The difference between the treatment groups in mean Hb from baseline to week 12 was 2.25g/dL (ANCOVA $p < 0.0001$). Hb increased to normal values at week 12 in 65% of ferric maltol group and 10% of placebo subjects. When the placebo subjects were transferred to ferric maltol treatment in the open-label phase, there was a sharp rise in Hb levels that mirrored the response in the ferric maltol group in the double-blind phase. There were further increases in Hb up to 48 weeks of treatment and no indication of any reduction in efficacy over the full 64 week treatment period.

Refer to the Investigator Brochure for further information.

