6.5 INDIVIDUAL WITHDRAWAL CRITERIA

Subjects have the right to withdraw consent without prejudice at any time during the study. If a subject withdraws consent, the Investigator should make a reasonable effort to determine the cause. All withdrawn subjects should have an End of Study Visit and a follow-up call 14 days after the last dose of study drug (if the subject agrees in the case of withdrawn consent).

Subjects who discontinue study treatment prior to Week 16 will be encouraged to continue with study visits and assessments up to and including assessments at week 16.

Subjects may be discontinued prematurely during the study for the following reasons:

- Withdrawal of informed consent.
- Unwillingness or inability to comply with protocol requirements.
- Pregnancy or not using a reliable method of birth control if female of childbearing potential.
- A ≥ 0.5 g/dL decrease from baseline in Hb that falls below 8.0g/dL on 2 consecutive weeks.
- Ferritin >700 ng/mL with a TSAT of $>50\%$ sustained for 2 consecutive weeks.
- SAEs that are judged by the Investigator to be related to study drug.
- Use of prohibited concomitant medications.
- Initiation of dialysis.
- Blood transfusions or donations for any cause.
- Any dose or frequency changes to myelosuppressants and/or ESAs (greater than 20% over an 8 week period) during the double-blind treatment period.
- Requirement for major surgery. Minor surgeries not associated with significant blood loss, in the Investigator's judgement, are permitted (e.g. surgery related to fistulae or vascular access, minor dental extractions, incision and drainage of abscess or simple excisions).

The reason for study drug discontinuation and the date of last dose should be recorded in the CRF.

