11.2.3 Sensitivity Analyses

For the primary endpoint, the following sensitivity analyses will be performed:

- The primary analysis defined in Section 12.2.1 (with multiple imputation) will be repeated using the per protocol (PP) population.
- The ANCOVA will be repeated for the ITT population but based on observed data only (complete case analysis without imputation).

- The ANCOVA will be repeated for the ITT population but using last observation carried forward (LOCF without imputation)
- A mixed model for repeated measures (MMRM) ANCOVA will be conducted using observed data only.

Other sensitivity analyses will be documented in the SAP.

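### Treatment arm is not among the variables listed for the primary multiple imputation; run as listed with data missing at random, the estimate shrinks and power falls by under 1 to about 8 points in the main cases examined

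*Combined protocol and SAP*

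**What the plan says.** Section 11.2.1 and the statistical part of the synopsis describe the primary analysis in almost the same words. Missing Week 16 changes are filled in by multiple imputation with 10 completed datasets. On the predictors the text says: "Hb concentrations at baseline, Week 4, Week 8 and gender will be considered as variables helpful in guiding this imputation". Each completed dataset then goes into an "ANCOVA with factors for treatment and disease and a covariate of baseline hemoglobin and eGFR", and the results are combined. The analysis set is all randomized subjects (11.3.3), so every missing Week 16 value passes through this imputation.

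Neither place names treatment arm as an imputation variable or says that imputation is done within arm. Sections 11.2.2 to 11.2.4 leave secondary methods, further sensitivity analyses and long-term imputation to the SAP. They do not expressly leave the primary imputation model to it. Section 8.3 requires a final SAP before the codes are released; no separate SAP text is in the document.

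On the amount of missing data, 11.1 says: "Assuming a drop-out rate of 20%, approximately 168 subjects total will be recruited". Section 4.4 reports for the earlier IBD trial that "87% and 82% ferric maltol and placebo treated subjects, respectively, completed the 12 week double blind period". Section 6.5 adds: "Subjects who discontinue study treatment prior to Week 16 will be encouraged to continue with study visits and assessments".

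**The concern.** An imputation model should contain at least the terms of the analysis that follows it. Here the term left out is the one the trial exists to estimate. If arm is absent, an imputed Week 16 value differs between arms only as far as hemoglobin at Weeks 4 and 8 already differs:

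- A subject with no post-baseline hemoglobin is imputed with no treatment effect at all.
- A subject missing only Week 16 is imputed from a Week 8 to Week 16 relation pooled over both arms. Week 12 is a telephone visit without a blood sample (9.2), so nothing later than Week 8 can help.

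Under missing at random the primary estimate is then too small. The pooled standard error is also too large for what the procedure does. At stake are the size of the reported effect and part of the planned power.

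**Working it through.** **1. The plan's own power figure.** Inputs from 11.1: difference 1.0 g/dL, SD 1.5, 90 and 45 evaluable subjects, two-sided 0.05.

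- SE = 1.5 × √(1/90 + 1/45) = 0.274.
- Power = Φ(1.0/0.274 − 1.96) = Φ(1.69) = 95.5%; with the noncentral t, 95.2%. The stated 95% reproduces.
- 135/0.8 = 168.75, against about 168 stated. At 2:1 this is 112 and 56.

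**2. All missing values arise before Week 4, arm omitted.** Let f₁ and f₀ be the missing fractions on active and placebo, and p the active share of the observed subjects. Setting the placebo mean to 0 and the true effect to 1.0, both arms' missing subjects are imputed around p. The expected difference is

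(1 − f₁) × 1.0 + (f₁ − f₀) × p.

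- 20% in both arms: 0.8 × 1.0 + 0 = 0.80 g/dL.
- 13% and 18%, from the 87% and 82% completion in 4.4: observed 112 × 0.87 = 97.4 and 56 × 0.82 = 45.9, so p = 0.68. Result: 0.87 − 0.05 × 0.68 = 0.84 g/dL. Overall missing is (2 × 13% + 18%)/3 = 14.7%, about 25 of 168.

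This step needs no assumption about correlations.

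**3. Simulation, first set of assumptions.** 112:56, true difference 1.0, SD of change 1.5. Sequential normal-regression imputation with 10 datasets, Rubin's rules with small-sample degrees of freedom, then ANCOVA on treatment, baseline hemoglobin and eGFR; 3,000 trials per case.

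Assumed, not in the documents: baseline SD 0.7; slope of change on baseline −0.3; SD of change 1.0, 1.25 and 1.5 and effect 0.35, 0.65 and 1.0 at Weeks 4, 8 and 16; autoregressive correlation 0.5, 0.7 or 0.85; random drop-out. Ranges are over the correlations. Monte Carlo error is about 0.3 to 0.6 points per power figure.

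| Week 16 missing | Timing | Estimate, arm omitted | Power, omitted v included, or loss |
|---|---|---|---|
| 20% | all before Week 4 | 0.79–0.80 | 86% v 93–94% |
| 20% | spread evenly | 0.84–0.86 | 90.5–92.0% v 95.3–95.5% |
| 20% | all after Week 8 | 0.89–0.95 | loss 0.7–1.7 points |
| 13%/18% | all before Week 4 | 0.83–0.84 | 91% v 95–96% |
| 13%/18% | spread evenly | 0.87–0.90 | loss 2.2–3.6 points |
| 13%/18% | all after Week 8 | 0.91–0.95 | loss 0.5–1.7 points |
| 10% | all before Week 4 | not tabulated | loss 2.1–2.4 points |
| 10% | spread evenly | not tabulated | loss 1.0–1.3 points |
| 10% | all after Week 8 | not tabulated | loss 0.2–0.6 points |

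With arm included, the estimate in the 20% cases is 0.99–1.01.

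**4. Standard error.** At 20% missing and correlation 0.7, the arm-omitted pooled SE against the empirical SD of the estimate is 0.278 v 0.225 (early), 0.270 v 0.236 (even) and 0.261 v 0.236 (late).

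**5. Drop-out that depends on observed hemoglobin.** Odds doubled per SD lower last value, about 19% missing. Arm omitted: 0.84–0.88 (even) and 0.89–0.93 (late). Arm included: 0.99–1.01.

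**6. Second set of assumptions.** Correlations of Week 4 and Week 8 change with Week 16 change of 0.6 and 0.75 (also 0.4/0.5 and 0.7/0.85); effects at Weeks 4 and 8 of 0.45 and 0.70 (also 0.25/0.50 and 0.50/0.80).

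- 20% before Week 4: 0.80 v 1.00 g/dL, power 86.2% v 93.9%, loss 7.7 points (SE 0.5).
- 10% after Week 8: 0.95 v 1.00 g/dL, power 97.2% v 98.0%, loss 0.8 points (SE 0.15); 0.65 to 1.4 over the alternatives.
- 20% after Week 8: loss about 1.6 to 4.2 points.
- 30% placebo and 15% active, all before Week 4: 0.74 g/dL, loss about 15 points.

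**7. No true effect.** At 20% missing and correlation 0.7 (first set), two-sided rejection with arm omitted is 1.6% (early), 2.5% (even) and 3.5% (late), against 5.0–5.3% with arm included.

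**The case against.** The strongest reply is that the sentence does not define an arm-free model. It names variables to be considered, does not say the list is complete, and a final SAP must exist before the codes are released. This stands: the omission from the text is certain, but the bias is conditional on the list being run as written. It does not remove the point, because nothing in the protocol hands the primary imputation model to the SAP.

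Second, the 8-point case is extreme. It needs a fifth of Week 16 values missing, all lost before the first post-baseline sample. The 20% in 11.1 is a planning drop-out rate and probably an upper figure for missing hemoglobin. Follow-up after stopping drug is encouraged, and 9.2 asks for the Week 16 assessments at early withdrawal, without saying how such a value enters the imputation. With the 4.4 completion figures and even timing the loss is 2.2–3.6 points, though the IBD trial differs in population and duration.

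Third, the range is not a bound. Weak correlations with a slow effect push the 10% late case to 1.4 points, and heavier placebo drop-out pushes the early case to about 15. This is right; the figures are illustrative.

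Fourth, shrinkage might be nearer the truth if subjects who stop drug lose their benefit. At 20% missing the all-randomized effect would be 1 − 0.2 = 0.80 if all benefit is lost, or 1 − 0.1 = 0.90 if half is lost. The documents give no figure for retained effect and state no such aim. An assumption of that kind should be declared, not arise from an omitted term.

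Fifth, three of the four sensitivity analyses in 11.2.3 (complete case, LOCF and MMRM) do not use this imputation. In the 20% cases the MMRM gave 0.99–1.01 g/dL with power 94–98%. They could expose a discrepancy but do not replace the primary result. The remaining one shares the flaw: "The primary analysis defined in Section 12.2.1 (with multiple imputation) will be repeated using the per protocol (PP) population" (the cross-reference evidently means 11.2.1).

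**Conclusion.** The concern holds and should be fixed. As listed, the primary imputation is narrower than the primary ANCOVA and lacks the treatment term. If it is run that way and data are missing at random, the estimate is pulled towards zero in every scenario tried. At a true 1.0 g/dL and up to 20% missing equally in both arms, it falls to roughly 0.80 when all loss is before Week 4 and to about 0.85–0.97 when all loss is after Week 8. The power loss in the main cases runs from under 1 point (10%, late) to about 8 points (20%, early).

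The early figure follows from arithmetic given equal drop-out. The others rest on assumed correlations, effect course and timing. The error is conservative and correctable, so it does not threaten a positive finding and is not fatal. The planned 95% power is itself correctly calculated.

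**What to change.** In 11.2.1 and the synopsis, and no later than the final SAP required by 8.3, add two sentences:

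- Imputation of Week 16 hemoglobin is done separately by treatment arm, or includes treatment as a model term; the per-protocol repeat uses the same model.
- This assumes data missing at random within arm, and would overstate the effect in all randomized subjects if those with missing values lost benefit after stopping drug.

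Baseline eGFR, which is in the ANCOVA but also not listed, may be added; it changed the estimate by at most 0.003.

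The cost is the two sentences and a by-arm option in the code. At correlation 0.7 and 20% missing spread evenly, by-arm imputation gives a pooled SE of 0.273 and power of 94.8%, against 0.270 and 95.3% with treatment as a term. Either choice is acceptable.
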